The PiezoWave 2 FBL 10x5 G2 device will be used to deliver extracorporeal shockwave therapy.

Safety and Tolerability

The device will only be used by trained staff members familiar will be device and deliverance of treatment. The environment of application of treatment will be equipped for emergency situations.

Ethics and Safety Reporting

Ethical approval will be sought from IRAS and the recruitment of participants will be in line with the declaration of Helsinki (2008). All patients will be informed of the study purpose, design, treatments, duration, risk and benefits and allowed to clarify additional questions during the consenting procedure. All participants must give informed consent and the consent form must be signed by the relevant parties, dated and kept with the

clinical trial forms in the patient's notes. The participant will be informed if any new information arises and informed consent must be gained again before carrying on with the trial.

The device will be used under the licensed indications and there are no anticipated adverse reactions. All adverse events or reactions and device failure will be reported on specific forms and action will be taken to treat the patient. If the event is deemed to be a serious adverse event or reaction the principal investigator will be informed within 24 hours. If an adverse event or reaction occurs the investigator will collect all possible information and the Principal Investigator will be informed to undertake the necessary action. Previous adverse reactions reported in the literature associated with extracorporeal shockwave therapy include: itching, burning, pain, skin pigmentation (12). Each participant will be given emergency contact details for the Principal Investigator if any concerns develop about the trial.

The trial will also comply with HEY research and development standards.

Withdrawals and Drop Outs

Patients are permitted to drop out at any point during the trial. The research investigators reserve the right to withdraw any participant if their health is at risk or if the participant fails to comply with the study protocol. If the subject develops an adverse event or reaction they will also be withdrawn from the trial.

Trial Exit

Participants will exit the trial completely when they complete the follow up period or if they:

- Withdrawn their consent to continue
- Withdrawn by the investigator due to health concerns or non-compliance

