- Undergo angioplasty, bypass grafting or further surgery
- Experience an adverse event or reaction
- Die

Overall timescale for the study

Recruitment will begin when Ethics and Trust Research and Development approval has been gained. The patients will be involved in the trial for 12 weeks.

Follow up assessments

Where possible all follow up will coincide with standard dressing and clinic follow ups to minimise the additional visits for participants. The follow up weeks are 4, 8, 12 after randomisation.

Data management

Data will be handled in line with the Data Protection Act 1998. The trial data will be registered with the local Data Protection officer.

For participants entering the study after the second amendment data will be handled in line with the GDPR 2018 guidelines. Patients will also be given information relating to this in the patient information sheets.

The data will be collected entered onto a excel spreadsheet created by the research team. The data will be kept on password protected NHS trust computers with firewalls and antivirus software on files with limited access to the trial investigators.

The storage of data will be in line with the IT department standards. Data will remain on the servers and be backed up on secure HEY IT systems. The data will be accessible to investigators and those seeking permission for monitoring and auditing.

Paper records will be stored and locked in the Academic Vascular Unit when not in use.

Study Report

The final pilot study report will outline the background, methods, results, discussion and conclusion of the trial in line with the CONSORT guidelines. The data from the participants will be anonymous. It will be submitted for publication in a peer-reviewed journal.

Administration

Participant Reimbursement

There is no provision for participant reimbursement. The trial follow up will coincide with routine follow up appointments.

Finance

Sponsors will not influence the trial or its publication.

References

1. Excellence NIoC. Clinical Care Summary: Diabetes - type 2. 2016.
3. Boulton AJ. The diabetic foot: grand overview, epidemiology and pathogenesis. Diabetes Metab Res Rev. 2008;24 Suppl 1:S3-6.
4. Excellence NIoC. Clinical Care Summaries: Diabetic Foot Problems: Prevention and Management. 2016.
5. Facts and Stats [press release]. October 2016.

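### Any adverse event, revascularisation or further surgery ends participation completely, with no rule for later outcome data, so week 4–12 and tolerability summaries can be selective and the follow-up rate can mix mandated exits with true loss

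*Combined protocol and SAP*

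**What the plan says.** Withdrawals and Drop Outs contains the rule "If the subject develops an adverse event or reaction they will also be withdrawn from the trial". Trial Exit repeats it in stronger form: "Participants will exit the trial completely when they complete the follow up period or if they" meet one of the listed conditions, which include "Undergo angioplasty, bypass grafting or further surgery" and "Experience an adverse event or reaction". Neither section sets a threshold of severity, seriousness or relatedness.

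Ethics and Safety Reporting says of the device that "there are no anticipated adverse reactions", yet a few sentences later it says: "Previous adverse reactions reported in the literature associated with extracorporeal shockwave therapy include: itching, burning, pain, skin pigmentation". Each of these would meet the exit wording.

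The event itself is documented. Ethics and Safety Reporting says "If an adverse event or reaction occurs the investigator will collect all possible information", and the Adverse events section records side effects throughout the study.

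Other provisions that bear on the point:

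- **Assessments, Follow-up:** the tolerability questionnaire belongs to the set of assessments after the third treatment. Imaging, quality of life and pain are repeated at weeks 4, 8 and 12. Infection and amputation are noted whenever the research team sees the participant.
- **Outcome measures:** follow-up rate and reasons for drop-out are both primary feasibility measures.
- **Method of Analysis:** outcomes are summarised at whatever follow-up points are available. Follow-up rates and known drop-out reasons are described. No denominator is stated.

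**The concern.** Exit depends on things the study sets out to measure. Pain is a patient outcome and a listed reaction. Amputation is a clinical outcome and is also further surgery. Tolerability is a secondary aim in the Synopsis, but a participant who reacts at session 1 or 2 is withdrawn before the questionnaire is due. The people who leave under the rule are therefore plausibly those doing worse or tolerating treatment less well, and the means, percentages and 95% confidence intervals at weeks 4, 8 and 12 describe those who remain.

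The follow-up rate is meant to inform a later trial. A participant the protocol removes has not shown that follow-up is infeasible, and the plan does not say how such a participant is counted. All three sessions fall within 7 days, so the rule mostly costs follow-up data rather than treatment exposure.

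**Working it through.** There is no figure in the plan to reproduce: the sample size of 40 is given without inputs, and no exit rate is stated. The steps below compare the rule with the schedule and then illustrate size.

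**1. What survives an exit.**

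| Item | Recorded at the exit event? | Planned after exit? |
|---|---|---|
| Adverse event or reaction | Yes | No outcome follow-up stated |
| Amputation or infection that triggers exit | Yes, as the event | Later events: none stated |
| Pain, quality of life, wound imaging | Only if already assessed | None stated |
| Tolerability score | Only if the post-third-treatment assessment was reached | None stated |

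**2. The only anchor in the documents.** The Introduction says 30–45% of diabetic digital amputations fail to heal, with 75% going on to higher amputation within the year. I read the 75% as applying to those that fail to heal.

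- Per year: 0.30 × 0.75 = 0.225 and 0.45 × 0.75 = 0.3375.
- Over 12 weeks at constant hazard, 1 − (1 − x)^(12/52): 0.057 and 0.091.
- Of 40 participants: 2.3 and 3.6, so about 2 to 4.

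This covers surgery only, and digital amputations only. The trial enrols any open foot wound with ABPI above 0.8, so the anchor may not apply. Exits for adverse events are not quantified anywhere.

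**3. Shift in a mean change.** Let e be the share exited and d the amount, in SD of change, by which leavers do worse than those who remain. If m is the mean of those who remain, the mean of all enrolled is (1 − e)m + e(m − d) = m − ed, so the shift is e × d. The 95% CI half-width is t(0.975, n − 1)/√n. Coverage of the all-enrolled mean uses a noncentral t with noncentrality ed√n. Both e and d are assumed.

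| e | n left | Shift, d = 0.5 | Shift, d = 1 | Half-width (SD) | Coverage, d = 0.5 / d = 1 |
|---|---|---|---|---|---|
| 5% | 38 | 0.025 | 0.05 | 0.329 | 94.7% / 94.0% |
| 10% | 36 | 0.05 | 0.10 | 0.338 | 94.0% / 91.0% |
| 20% | 32 | 0.10 | 0.20 | 0.361 | 91.5% / 80.5% |
| 30% | 28 | 0.15 | 0.30 | 0.388 | 88.1% / 66.6% |

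The first two rows bracket the anchor. The last two have no support in the documents. The shift is zero if d = 0 and reverses if leavers do better. Data before exit still count, so weeks 4 and 8 lose no more to these exits than week 12.

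**4. Follow-up rate.** Suppose 32 of 40 reach week 12: 80% (exact 95% CI 64–91%).

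- With 8 mandated exits and no other loss, 32/32 = 100% (89–100%) of those still allowed to attend were followed.
- With 4 mandated exits and 4 other losses, 32/36 = 89% (74–97%).

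The same headline rate supports different plans for a later trial unless the split is shown.

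**5. Tolerability.** If a share r exits for a reaction before the post-third-treatment assessment, 40 × r scores are missing: 1, 2, 4 or 8 for r = 2.5%, 5%, 10% or 20%. These only restate the assumed r.

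**The case against.** The strongest reply is that the planned report already handles much of this. Reasons for drop-out are a primary measure beside the follow-up rate, the two are to be presented together, the team would know the reason for any exit it imposes, and the Study Report section commits to CONSORT. A reader might infer that the follow-up rate cannot be interpreted at all. The documents do not support that. What remains is an unstated denominator and no statement that mandated exits are shown apart from other losses.

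A reader might also infer that the amputation or reaction which triggers exit goes uncounted. It does not: the event is recorded. What is lost is anything later in the same person. Nor are early leavers barred from interview, since interviews follow the last treatment rather than the third; the plan simply does not say whether they are approached.

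It is also fair to say that the larger figures rest on assumption. Coverage of 67% needs 30% exits and a 1 SD difference together, and neither comes from the documents. In a single-arm descriptive study with no hypothesis test, coverage decides little. For wound volume, leaving out measurements after revascularisation is a reasonable choice in its own right.

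Two limits on the text should be kept in view. The sentence placing the tolerability questionnaire is incomplete, so its timing after the third treatment is the natural reading rather than an explicit one. The patient information sheets are not available here and might address data after withdrawal.

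What stands is that the protocol, as written, ends all outcome collection for reasons tied to the outcomes, and event forms do not replace pain, quality-of-life, wound or tolerability data.

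**Conclusion.** The point holds in a limited form and should be fixed. The exit rule is complete, has no threshold, and has no accompanying provision for outcome data. Following it as written can make the week 4–12 and tolerability summaries selective, and the follow-up rate mixes mandated exit with loss unless the two are separated.

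The size is unknown. At 5–10% exits, which bracket the surgical anchor of about 6–9%, and with leavers 0.5–1 SD worse (assumed), means shift by 0.025–0.10 SD against a half-width of about 0.33–0.34 SD: modest. Larger effects are possible if adverse-event exits are common, but nothing in the documents shows that they will be. The clearest consequences are structural: missing tolerability scores for early reactors and an undefined denominator for a primary measure.

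**What to change.** Reconcile Assessments, Adverse events, Withdrawals and Drop Outs, and Trial Exit so that the end of study treatment is distinct from the end of data collection. No rule on stopping treatment is proposed.

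- After exit for an adverse event or reaction, revascularisation or further surgery, and unless consent is withdrawn, continue to collect infection, amputation, adverse events, pain, quality of life and wound status to week 12.
- Obtain the tolerability score from everyone who received at least one session.
- State the follow-up-rate denominator as all enrolled, and tabulate mandated exits by reason, separately from other losses.
- Flag wound volumes taken after revascularisation or surgery. They may be left out of the main wound summary without ending the other outcomes.

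The cost is a protocol amendment, with revised information sheet and consent wording; Ethics and Safety Reporting already says that, when new information arises, "informed consent must be gained again before carrying on with the trial". Visit burden is small because follow-up is meant to coincide with routine appointments where possible. The Patient Consent section refers to participants already in the study, so follow-up will have run under two rules, and this should be reported. Assessments already missed cannot be recovered, although later amputations might be found in hospital records, subject to consent.
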